DEPT. OF ANESTHESIOLOGY AND INTENSIVE THERAPY

Head of Department: [name], PhD

[contact]

[contact]

E-mail: [contact]

Transfusion Practices in Intensive Care Units: a Hungarian Nationwide Survey

STUDY PROTOCOL WITH SAP

Approval Number: BM/8863-3/2025

Last updated on June 4, 2025

Introduction

Blood transfusion, as a life-saving therapeutic intervention, is an essential part of patient care. However, like any therapeutic procedure, transfusion carries potential risks and complications; therefore, its indication must always be carefully considered. The decreasing number of blood donors and inadequate blood utilization represent an increasing global problem by limiting access to blood products, while the costs of producing and storing blood products place a significant burden on healthcare budgets.

According to data from the Hungarian Central Statistical Office, in 2022 a total of 541,402 units of blood products were used in Hungary for patient care and transfusion purposes.

In a recently published international prospective cohort study involving 223 intensive care units, transfusion rates were found to be high among critically ill patients during the study period (2019–2022). Twenty-five percent of patients received at least one unit of red blood cell transfusion (median: 2 units/patient) during their ICU stay.

This is not surprising, as beyond bleeding complications and overt or occult hemorrhage, critically ill patients have numerous additional risk factors for anemia. The most common include myelosuppression associated with critical illness, chronic iron deficiency, renal failure, and iatrogenic blood loss related to invasive diagnostic and therapeutic procedures as well as laboratory testing.

Based on results from previous randomized controlled trials, current recommendations and guidelines favor a restrictive transfusion strategy (indicated below hemoglobin levels of 7–8 g/dL) over a liberal approach (9 g/dL) in critically ill patients.

It is important to emphasize that the goal of red blood cell transfusion is not solely to normalize hemoglobin levels, but to ensure adequate tissue oxygenation by optimizing oxygen transport capacity. Given the significant heterogeneity of ICU patient populations, individual assessment is essential in all cases. Therefore, a single laboratory parameter—hemoglobin concentration—is insufficient to determine transfusion indication and required dose. In other words, not only the degree of anemia but its consequences determine the need for transfusion.

Assessment should include clinical signs (e.g., general weakness, dizziness, tachycardia, circulatory failure, dyspnea, failed weaning, etc.) and physiological parameters reflecting impaired tissue oxygenation and oxygen deficit/debt (e.g., serum lactate, central venous oxygen saturation, arterio-venous carbon dioxide difference, arterio-venous oxygen content difference).

Patient Blood Management (PBM) focuses on the triad of anemia, blood loss, and transfusion, emphasizing opportunities to modify these factors. Implementation of PBM programs and dedicated outpatient clinics has improved patient safety and reduced blood utilization in many countries. Although Hungary has introduced a National Blood Donation and Blood Saving Program and professional guidelines for managing life-threatening perioperative bleeding, these mainly focus on high-volume bleeding and hemostasis correction. PBM, however, extends beyond this and is also highly relevant in ICU care, even in non-bleeding patients.

The aim of the present questionnaire-based survey is to assess daily transfusion practices in Hungarian ICUs. To our knowledge, no similar survey has previously been conducted in Hungary.

Study Location

Flór Ferenc Hospital, Kistarcsa

Department of Anesthesiology and Intensive Care

[name]

Investigators

[name], PhD – Head of Department, Study Director

[name] – Senior Physician, Investigator

[name] – Senior Physician, Transfusion Responsible, Investigator

[name] – Resident, Co-investigator

Aim of the Study

The aim is to assess transfusion practices in the management of anemic critically ill patients in Hungarian ICUs using an online questionnaire consisting of 15 mandatory and 1 optional question. The study evaluates the use and frequency of physiological transfusion triggers (e.g., serum lactate, ScvO₂, CO₂ gap, oxygen content difference) and the implementation of PBM programs.

The results may contribute to improving transfusion practices, enhancing patient safety, improving outcomes, and promoting rational blood use.

Study Type

Non-interventional, cross-sectional observational survey study.

Participants

Physicians working in Hungarian ICUs

Planned number: minimum 100 respondents

Participation is voluntary and anonymous.

Inclusion Criteria

Registered anesthesiology and intensive care residents, trainees, and specialists working in Hungary.

Exclusion Criteria

Anesthesiologists and intensive care practitioners working in non-Hungarian intensive care units.

Funding

No special equipment or financial resources required.

Methods

A descriptive online questionnaire (Google Forms) in Hungarian. No personal or sensitive data are collected. Institutional names are recorded only for geographical analysis. Data collection period: July 1 – September 30, 2025.

Information for Respondents

Dear Colleague,

Transfusion is essential but carries risks. Current evidence supports restrictive strategies. However, Hungarian data on ICU transfusion practices are limited, which is why this survey is conducted.

The questionnaire takes approximately 10–15 minutes. Participation is voluntary and anonymous.

Contact: [contact]

Questionnaire Structure (Summary)

- Type of institution
- Institution and department name
- Years of professional experience
- ICU profile
- Number of ICU beds
- Annual patient volume
- Use of PBM protocol
- Presence of PBM clinic
- Local transfusion protocol
- Transfusion practices (1 vs 2 units)
- Clinical indications
- Hemoglobin thresholds
- Physiological triggers (e.g., lactate, ScvO₂, CO₂ gap)
- Target hemoglobin and physiological values

Endpoints

Primary endpoint:

Use of physiological parameters in transfusion decision-making.

Secondary endpoints:

- Restrictive vs liberal transfusion strategy
- PBM implementation
- Relationship between PBM and transfusion triggers
- Presence of local protocols

Statistical Analysis Plan

Data analyzed using MedCalc software. Results expressed as percentages with 95% confidence intervals. Normality tested with Kolmogorov–Smirnov test. Group comparisons via chi-square test, correlations via Pearson method, and PBM effects via two-way RM ANOVA. Significance: $p < 0.05$.

Publication Policy

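### A survey titled nationwide has no list of ICUs, no denominator and no coverage measure, so its percentages and 95% CIs describe self-selected respondents

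*Combined protocol and SAP*

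**What the plan says.** The target of inference is national. The title is "Transfusion Practices in Intensive Care Units: a Hungarian Nationwide Survey", and the Introduction closes with the aim: "The aim of the present questionnaire-based survey is to assess daily transfusion practices in Hungarian ICUs".

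The recruitment text is short. Under Participants the population is "Physicians working in Hungarian ICUs", with "Planned number: minimum 100 respondents" and "Participation is voluntary and anonymous". The Inclusion Criteria admit "Registered anesthesiology and intensive care residents, trainees, and specialists working in Hungary". The Exclusion Criteria remove only "Anesthesiologists and intensive care practitioners working in non-Hungarian intensive care units". Methods describes the instrument as "A descriptive online questionnaire (Google Forms) in Hungarian" and limits the use of institution names to a geographical analysis.

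The questionnaire asks for institution type, institution and department name, ICU profile, number of beds and annual volume. The Statistical Analysis Plan reports percentages with 95% confidence intervals. It uses none of these items to measure coverage or to compare responding ICUs with all Hungarian ICUs.

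**The concern.** The target (ICUs in Hungary) and the sample (physicians who opt in) are not linked by any rule. A hundred eligible physicians from a few interested centres would satisfy the plan. Without a count of ICUs or of eligible physicians, neither a response rate nor a coverage figure can be calculated, so a reader cannot judge how far the respondents resemble the country.

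This bears directly on the primary endpoint, the use of physiological parameters in transfusion decisions. Physicians interested in that topic could plausibly be readier to complete a questionnaire on it. A 95% CI does not reflect that kind of error, and recruiting more volunteers only narrows the interval around the same, possibly displaced, value.

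A smaller point is that nothing bars the four listed investigators or their department from responding. The Introduction argues that hemoglobin alone is not enough and that physiological parameters should be assessed, so they have a published position on the primary endpoint.

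**Working it through.** **The plan's own figure.** The minimum of 100 comes with no expected proportion, precision target or population size, so it cannot be reproduced from the documents. If one assumes a proportion of 50% and a half-width of 10 points, n = 1.96² × 0.5 × 0.5 / 0.10² = 96.04, rounded up to 97, which is close to 100. The number is therefore not shown to be wrong as a precision target. The check below concerns what that precision leaves out.

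**Inputs.** From the documents: n = 100 (the stated minimum), a 95% interval, voluntary response. Assumed, because the documents give none of them: 70% of respondents use physiological parameters; the response rate r is 10%, 30% or 50%; the gap g between responders and non-responders is 10, 20 or 30 points, or the reverse.

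**Interval the survey would report.** Half-width = 1.96 × √(0.70 × 0.30 / 100) = 0.090, so the CI is about 61–79%.

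**True value in the eligible population.** True = r × 70% + (1 − r) × (70% − g) = 70% − (1 − r) × g. At r = 30%:

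- g = 10: 0.3 × 70 + 0.7 × 60 = 63%
- g = 20: 0.3 × 70 + 0.7 × 50 = 56%
- g = 30: 0.3 × 70 + 0.7 × 40 = 49%

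The full range, with a negative gap meaning that non-responders use the parameters more often:

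| Gap g (points) | r = 10% | r = 30% | r = 50% |
|---|---|---|---|
| 30 | 43% | 49% | 55% |
| 20 | 52% | 56% | 60% |
| 10 | 61% | 63% | 65% |
| −10 | 79% | 77% | 75% |
| −20 | 88% | 84% | 80% |

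At r = 30% the interval misses the true value only when the gap exceeds 0.090 / 0.7, about 13 points in either direction. A 10-point gap leaves the truth inside; a 20-point gap puts it outside.

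**More respondents.** At n = 400 the half-width falls to 1.96 × √(0.21 / 400) = 0.045, but (1 − r) × g does not change.

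**Investigators as respondents.** Four of 100 is 4% of the sample. If all four were among 70 users, removing them gives 66/96 = 68.75%, a shift of 1.25 points against a half-width of 9. The size of the rest of their department is not given.

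**The case against.** Voluntary questionnaires are ordinary practice, Methods calls this one descriptive, and participants are defined as physicians. The SAP nowhere promises weighted national estimates. Institution and department names are collected, so responding ICUs could be counted afterwards. These points are fair, but they do not supply the national total to divide by. Methods also confines the names to geographical use, and the title and aim still point to the country as a whole.

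Several stronger readings are tempting and are not supported:

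- A reader might infer that the primary proportion will be inflated. The documents give no response rate, gap or direction, so only possible bias can be claimed. With a gap under about 13 points at 30% response, the CI still contains the truth.
- A reader might infer that anyone can answer, or that the sample is fixed at 100. Eligibility is limited to registered residents, trainees and specialists in the field, and 100 is a minimum.
- A reader might infer that the investigators would be answering a survey whose hypothesis they know. No hypothesis is stated, nothing says they will respond, and the effect of four answers is small.
- A reader might infer that standardising to institution type, or reaching a set share of ICUs, would restore the national claim. Neither removes selection by interest within an ICU: one enthusiast in each of half the ICUs would pass a 50% coverage rule with the same bias.

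**Conclusion.** The point holds as a limit on what the survey can conclude. Followed exactly, the plan produces percentages for self-selected eligible physicians, with intervals that cover sampling error only, under a title and aim that invite a national reading. That rests on the text alone and needs no assumption.

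The size of any bias does rest on assumptions. With 70% observed and 30% response, gaps of 10 to 30 points correspond to true values from 63% down to 49%, against a CI of about 61–79%; a gap in the other direction would move the truth upward. The documents cannot say which case applies, and without a denominator the finished survey could not say either. The investigator issue is secondary and worth addressing only because doing so is simple.

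**What to change.** 1. Send the link to a fixed list of all Hungarian ICUs and record the number invited. Report the share of ICUs with at least one response, overall and by institution type, and the number of respondents per ICU. Widen the Methods sentence that restricts institution names to geographical analysis so that it allows this.
2. State the primary conclusion as applying among responding physicians, with coverage reported beside it. Set no coverage threshold that unlocks a national claim.
3. As a sensitivity analysis only, give the primary proportion standardised to the list's mix of institution types, noting that this does not correct selection by interest.
4. Ask the investigators not to respond, and repeat the primary result without the study department.

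The cost is one external ICU list that includes institution type, a small change to the protocol and SAP text, a somewhat wider interval for the standardised estimate, and a softer nationwide claim. No new questionnaire item is needed. If the collection period in Methods (July 1 to September 30, 2025) has already passed, the number invited can be given only if it was recorded. ICU coverage against a list, the restricted wording, the standardised estimate and the repeat without the study department remain possible and should be declared post hoc.

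### The analysis makes no allowance for several respondents from one ICU; if colleagues' answers are correlated, intervals will be too narrow and tests of ICU-level factors such as PBM will reject too often

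*Combined protocol and SAP*

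**What the plan says.** The Participants section defines the unit of response as the individual: "Physicians working in Hungarian ICUs", with "Planned number: minimum 100 respondents". Under Inclusion Criteria all grades are eligible: "Registered anesthesiology and intensive care residents, trainees, and specialists working in Hungary". No section limits the number of respondents per ICU or says how several answers from one ICU are handled.

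The Questionnaire Structure collects "Institution and department name", so a cluster identifier will exist. The Methods restrict its purpose: "Institutional names are recorded only for geographical analysis". Each physician is also asked about features of the unit or institution, including "Use of PBM protocol", the existence of a PBM clinic and a local transfusion protocol. Three of the four secondary endpoints rest on these items: PBM implementation, the relation of PBM to transfusion triggers, and the presence of local protocols.

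The Statistical Analysis Plan is one short paragraph. It gives "Results expressed as percentages with 95% confidence intervals" and "Group comparisons via chi-square test", then Pearson correlations, a two-way repeated-measures ANOVA for PBM effects, and a 0.05 significance level. It names no cluster-robust variance, mixed model, GEE, design effect or analysis at ICU level.

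**The concern.** Physicians in one ICU share a local protocol, monitoring equipment and PBM arrangements, so their answers may well resemble each other. A second answer from the same unit then carries less information than one from a new unit, and an analysis that treats all answers as independent overstates the information.

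The consequence is greatest where the explanatory factor belongs to the ICU, because the comparison is then really between ICUs. PBM status, local protocol and ICU profile are of this kind. An association between PBM and the use of physiological triggers could be declared significant because a few units with many respondents happen to differ. For PBM implementation itself, five colleagues who report the same programme are close to one observation. The errors go in the favourable direction: more apparent precision and smaller p-values.

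**Working it through.** **No figure to reproduce.** The plan states no precision target, power, effect size, ICC or cluster size behind its minimum of 100.

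**Inputs.** From the documents: N = 100 (the stated minimum), 95% intervals, 0.05 level (taken as two-sided). Assumed: true percentage 50%, equal numbers m of respondents per ICU, and ICC 0.1 to 0.3, with lower values also shown.

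**Formulas.**
- Design effect: DEFF = 1 + (m − 1) × ICC
- 95% half-width: 1.96 × √(0.25 × DEFF / 100)
- True coverage of the unadjusted interval: 2Φ(1.96/√DEFF) − 1
- True size of a nominal 5% test of an ICU-level factor: 2 × [1 − Φ(1.96/√DEFF)]

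**Reference under independence.** DEFF = 1, so the half-width is 1.96 × √(0.25/100) = 9.8 points.

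| m | ICC | DEFF | Half-width (points) | Coverage of unadjusted interval | Size, ICU-level factor |
|---|---|---|---|---|---|
| 1 | any | 1.00 | 9.8 | 95.0% | 5.0% |
| 2 | 0.05 | 1.05 | 10.0 | 94.4% | 5.6% |
| 2 | 0.1 | 1.10 | 10.3 | 93.8% | 6.2% |
| 2 | 0.3 | 1.30 | 11.2 | 91.4% | 8.6% |
| 4 | 0.1 | 1.30 | 11.2 | 91.4% | 8.6% |
| 4 | 0.3 | 1.90 | 13.5 | 84.5% | 15.5% |

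Worked line for m = 4, ICC 0.3: DEFF = 1 + 3 × 0.3 = 1.9; half-width = 1.96 × √(0.25 × 1.9/100) = 13.5 points.

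**Simulation of the chi-square test.** Beta-binomial answers, 100 respondents, 50% prevalence, factor assigned at ICU level to about 30% of ICUs, no true association, ICC 0.1 to 0.3:
- 50 ICUs × 2: rejects in about 6–9% of runs
- 25 ICUs × 4: about 9–17%
- 1 per ICU: about 5%

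Splitting the ICUs half and half gives 6.9–9.8% at two per ICU and 9.4–16.7% at four. The baseline there is already 5.7–5.9% at one per ICU, because the counts are discrete.

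**Factor varying within the ICU.** When the factor is assigned to physicians independently of their ICU, the same simulated test stays at 4.8–5.8% over all settings tried (1 to 10 per ICU, ICC 0.05 to 0.3). The inflation is therefore specific to ICU-level factors.

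**Pure ICU attribute.** If all colleagues report the same PBM status, the ICC is 1 and DEFF = m. At m = 2 the half-width is 13.9 points and the unadjusted interval covers 83.4%; at m = 5, 21.9 points and 61.9%.

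**The ANOVA.** These test sizes describe the chi-square test. They were not computed for the repeated-measures ANOVA, which models repeated answers within one respondent and not similarity between colleagues. PBM status is a between-respondent factor there, so the same mechanism applies, but its size has not been calculated.

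**The case against.** Five points can be made for the plan.

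- **The effect is conditional.** It needs more than one respondent in at least some ICUs and a positive ICC, and the documents give neither. At two per ICU and an ICC of 0.05 or less, the size stays near 5–6%. This stands. A reader might infer that the intervals and p-values are bound to be wrong, or that a large inflation is established; the documents do not support that. They show only that the plan neither prevents nor checks the conditions.
- **PBM effects are assigned to the ANOVA, not clearly to chi-square.** This stands as a limit on what the chi-square figures describe. It does not rescue the plan, because that ANOVA ignores correlation between colleagues as well.
- **Not every comparison is affected.** A reader might infer that all chi-square tests are inflated. Years of experience varies within an ICU, and tests of such factors stay near 5%. PBM and protocol items are also self-reported, so colleagues may disagree, which weakens the worst case without removing it.
- **The sentence on institutional names follows a statement that no personal data are collected, so it may be a privacy assurance rather than an analysis rule.** That is a fair reading. Even so, the stated purpose does not cover use as a cluster identifier, and the Statistical Analysis Plan supplies no clustered method.
- **The survey is described as descriptive.** The plan nevertheless sets a significance threshold and a PBM–trigger endpoint, and descriptive percentages still carry intervals.

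**Conclusion.** The concern holds in conditional form. The plan allows any number of physicians per ICU and names no method that respects within-ICU correlation. If several colleagues per ICU answer alike, the intervals for percentages, including the primary endpoint, will be too narrow, and tests of ICU-level factors will be too liberal.

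Under the assumed ICC of 0.1 to 0.3 with 100 respondents, the inflation is modest at two per ICU and material at four, where true size is roughly two to three times nominal. It vanishes at one per ICU. The direction is secure once ICUs contribute several correlated answers; the size is not, and it can be judged only when the spread of respondents over ICUs is known.

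**What to change.** **Methods and respondent information.** State that institution/department is converted to a code and used both for geographical analysis and as the cluster identifier, and align any matching assurance to respondents. Confirm that this item is mandatory: the Aim of the Study mentions one optional question without naming it, and a missing identifier would leave clusters incomplete.

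**Statistical Analysis Plan.**
- Compute intervals for physician-level percentages with department-clustered variance.
- Test ICU-level factors, including the PBM–trigger relationship now assigned to the ANOVA, with mixed logistic regression, GEE with a small-sample correction, or a Rao–Scott test.
- Report PBM implementation and local-protocol presence once per ICU, with a stated rule for discordant answers.
- Report the number of ICUs and the distribution of respondents per ICU.

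**A limit of the remedy.** With few and very uneven ICUs, robust tests stay liberal. In a simulated case of 30 ICUs with 1 to 15 respondents each, an uncorrected cluster-robust test rejected in about 11% of runs, against 11.9% (ICC 0.1) and 23.1% (ICC 0.3) for chi-square. A simple correction with a t reference still left about 10%. The small-sample correction should be named in advance, and results from such a pattern read with caution.

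**Cost.** Somewhat wider intervals, a minor protocol wording amendment (with whatever approval that needs), and possibly software other than MedCalc; whether MedCalc supports these methods should be checked. No extra respondents or questions are needed.

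### The respondent letter endorses restrictive transfusion before a self-report questionnaire that measures restrictive versus liberal practice, and is liable to inflate the restrictive share

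*Combined protocol and SAP*

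**What the plan says.** The section Information for Respondents is the letter to participating physicians. After a sentence describing transfusion as necessary but not free of risk, it says "Current evidence supports restrictive strategies". It then gives the reason for the survey: "However, Hungarian data on ICU transfusion practices are limited, which is why this survey is conducted".

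The Questionnaire Structure (Summary) lists 14 topics. "Hemoglobin thresholds" is the twelfth and "Target hemoglobin and physiological values" the fourteenth. Under Endpoints, "Restrictive vs liberal transfusion strategy" is the first secondary endpoint; the primary endpoint is "Use of physiological parameters in transfusion decision-making".

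The Introduction gives the only numerical meaning of the two strategies, saying that current guidance and recommendations "favor a restrictive transfusion strategy (indicated below hemoglobin levels of 7–8 g/dL) over a liberal approach (9 g/dL) in critically ill patients". It closes with the purpose: "The aim of the present questionnaire-based survey is to assess daily transfusion practices in Hungarian ICUs".

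All data come from one online form. Participation is anonymous, although institution and department names are recorded.

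**The concern.** The survey sets out to describe what physicians do. For the restrictive-versus-liberal endpoint the only evidence of that is what they say they do. A letter from the study team naming one of the two categories as supported by evidence is a leading introduction. A physician whose habits are liberal, or mixed, gets a cue about which answer the authors regard as sound.

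The expected direction is one-sided, towards a higher reported restrictive share. The plan has no means of detecting it: no group receives a different introduction, no answers are checked against transfusion records, and no sensitivity analysis addresses socially desirable answers. The Statistical Analysis Plan reports percentages with 95% confidence intervals, which reflect sampling error only, so a shift of this kind would not show in the published interval.

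**Working it through.** **Is the letter a cue for a measured endpoint?** Set side by side, the letter names restrictive strategies as the supported ones, and the secondary endpoint classifies respondents as restrictive or liberal. The same word appears in both. The next sentence of the letter, on the lack of Hungarian data, explains the survey without help from the evidence statement.

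**Which items are exposed?** The haemoglobin threshold item is clearly exposed. The sentence gives no haemoglobin value and does not mention single versus double units, target haemoglobin or physiological parameters, so any effect on those items is inference.

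**How large could it be?** The plan gives no figure to reproduce: the minimum of 100 respondents comes without an expected proportion or target precision. What follows is illustration.

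Inputs: *n* = 100 (Participants); 95% confidence interval (Statistical Analysis Plan); true restrictive share *p* = 0.70 (assumed); share *f* of truly liberal respondents who report a restrictive threshold = 0.10 (assumed).

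1. Reported share: *q* = *p* + *f*(1 − *p*) = 0.70 + 0.10 × 0.30 = 0.73. Bias *b* = 0.03, or 3 points.
2. Standard error at the reported share: √(0.73 × 0.27 / 100) = 0.0444. At the true share: √(0.70 × 0.30 / 100) = 0.0458.
3. Coverage: Φ(1.96 − *b*/SE) − Φ(−1.96 − *b*/SE). With SE 0.0444, *b*/SE = 0.676 and coverage is 89.6%. With SE 0.0458, *b*/SE = 0.655 and coverage is 90.0%.
4. Exact binomial coverage of the Wilson interval in the same setting: 88.8%. Without any misreporting it is 93.7%, slightly under 95% because the count is discrete.

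So coverage is about 89 to 90%, and the 3-point shift compares with a half-width of 1.96 × 0.0458 = 9.0 points.

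Range over the assumptions (bias in points; Wilson coverage, *n* = 100):

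| True share | *f* = 5% | *f* = 10% | *f* = 20% | *f* = 30% |
|---|---|---|---|---|
| 50% | 2.5; 91% | 5.0; 82% | 10.0; 46% | 15.0; 13% |
| 70% | 1.5; 93% | 3.0; 89% | 6.0; 72% | 9.0; 44% |
| 80% | 1.0; 94% | 2.0; 92% | 4.0; 83% | 6.0; 66% |

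**Would more respondents help?** No. The bias does not depend on *n*, while the interval narrows around the wrong value. With 400 respondents at *p* = 0.70 and *f* = 0.10, SE = √(0.73 × 0.27 / 400) = 0.0222, *b*/SE = 1.35, and coverage falls to about 73%.

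**The case against.** Participation is anonymous, and the letter says so, which limits the pressure to give an approved answer. Recording institution and department weakens that protection without removing it. Respondents are residents, trainees and specialists in the field, and the Introduction itself describes the restrictive preference as current guidance. Many will know it already, so one more sentence may change little. A respondent who is already restrictive cannot be moved on a two-category endpoint. All of this stands: the effect may be small, and the documents contain no evidence of its size.

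Four stronger readings are tempting and go beyond the documents.

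- A reader might infer that the cue comes immediately before the threshold question. It precedes the whole form, and 11 of the 14 listed topics come first. The questionnaire is shown only in summary, so item wording and screen layout cannot be checked.
- A reader might infer that the letter portrays transfusion as harmful. The sentence before the evidence statement is two-sided, calling transfusion essential as well as risky.
- A reader might infer that the survey's main result is compromised. The primary endpoint concerns physiological parameters, which the sentence does not mention. Nor do the documents state measuring departures from guidelines as an objective.
- A reader might assume a shift of 5 or 10 points and conclude that coverage collapses. With a true share of 70%, such shifts need one sixth (5/30) and one third (10/30) of truly liberal respondents to misreport. Coverage would then be about 79% and 29% by the normal approximation with the standard error at the shifted share. Nothing in the documents supports misreporting on that scale.

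**Conclusion.** The point holds as a risk of bias in one secondary endpoint. The sentence is in the respondent-facing text, it favours one category of a self-reported outcome, and nothing elsewhere in the plan offsets it. The likely direction is over-reporting of restrictive practice.

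That bias occurs, and how much, is not established. The 3-point shift with about 90% coverage rests on an assumed true share of 70% and assumed misreporting by 10% of truly liberal respondents; neither comes from the documents. Because all respondents read the same text, the survey's own data cannot supply the missing estimate. The case for acting therefore rests on how easily the risk can be avoided, not on a demonstrated large effect.

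**What to change.** The document was last updated on June 4, 2025 and data collection is planned from July 1, so the form can be changed before launch:

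- Remove the evidence sentence from the letter. Keep the sentence on limited Hungarian data, adjusting its opening word so that it reads on its own.
- Add a neutral introduction, for example: *This survey describes how transfusion decisions are currently made in Hungarian ICUs; there are no right or wrong answers.*
- Put any statement about the evidence on the page shown after submission.

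If the form has already been used, report the letter's wording as a limitation and interpret the restrictive share as a likely upper estimate.

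The cost is a small edit to the online form and, if needed, a notification to the approving body. Sample size and precision are unaffected.

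### Local-protocol, PBM-clinic and PBM-protocol results have no stated unit of analysis; counted per physician, they weight ICUs by number of respondents and carry intervals that are too narrow

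*Combined protocol and SAP*

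**What the plan says.** The Introduction sets the target: "The aim of the present questionnaire-based survey is to assess daily transfusion practices in Hungarian ICUs". Under Participants, the people sampled are "Physicians working in Hungarian ICUs", and the size is "Planned number: minimum 100 respondents". The Inclusion Criteria admit "Registered anesthesiology and intensive care residents, trainees, and specialists working in Hungary". Nothing caps the number of responses from one ICU.

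The secondary endpoints include PBM implementation and "Presence of local protocols". The questionnaire summary also asks each respondent whether a PBM clinic exists and whether there is a local transfusion protocol. It records "Institution and department name", so responses from the same unit could be recognised, but the Methods section says institution names are kept for geographical analysis alone.

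The only instruction on summarising these items is in the Statistical Analysis Plan: "Results expressed as percentages with 95% confidence intervals". No denominator is named. There is no step that reduces responses to one per ICU, reconciles conflicting answers from one ICU, weights, or allows for clustering.

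**The concern.** A local transfusion protocol or a PBM clinic either exists in a given unit or hospital or does not. If seven colleagues report it, that is one fact reported seven times. A percentage over respondents gives the share of responding physicians whose workplace has the protocol, with each ICU weighted by how many of its staff replied. The stated aim leads a reader to take it as the share of ICUs.

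Two consequences follow. First, the respondent percentage can differ from the ICU percentage if ICUs with the protocol supply more, or fewer, respondents than the others; a larger sample does not remove that difference. Second, an ordinary binomial interval treats colleagues' reports of one fact as independent, so it overstates precision. In addition, two colleagues who disagree about the same protocol would both be counted, one as yes and one as no, with no rule to settle it.

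**Working it through.** **Inputs from the documents.** Minimum 100 respondents; physicians as the sampled unit; no cap per ICU; no denominator in the SAP. The figure of 100 comes without a rate, precision or power, so there is no calculation to reproduce. For reference, with 100 independent respondents and a percentage of 50%, the half-width is 1.96 × √(0.5 × 0.5 / 100) = 9.8 points.

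**Assumptions.** The documents do not give the number of responding ICUs (K) or the respondents per ICU, so both are varied. Responding ICUs are treated as a sample from a large number of ICUs.

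**Interval width.** With equal numbers m = 100/K per ICU and within-ICU correlation ICC, the design effect is deff = 1 + (m − 1) × ICC. The effective sample size is 100/deff, and the actual coverage of the naive 95% interval is 2Φ(1.96/√deff) − 1. With full agreement inside each ICU (ICC = 1), deff = m and the effective size is K. At 50%:

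| ICUs (K) | m | deff | Effective n | Half-width needed | Coverage of the naive ±9.8 points |
|---|---|---|---|---|---|
| 80 | 1.25 | 1.25 | 80 | 11.0 | 92% |
| 50 | 2 | 2 | 50 | 13.9 | 83% |
| 40 | 2.5 | 2.5 | 40 | 15.5 | 79% |
| 20 | 5 | 5 | 20 | 21.9 | 62% |

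For K = 40, for example, 1.96/√2.5 = 1.24, which gives coverage of about 79%. With weaker agreement (ICC = 0.5) the loss is smaller: deff is 1.75 with 40 ICUs (coverage 86%) and 3.0 with 20 ICUs (74%).

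**Point estimate.** The respondent percentage minus the ICU percentage equals Cov(respondents per ICU, status) / mean respondents per ICU. Take 40 ICUs, 10 with 7 respondents and 30 with 1, so 70 + 30 = 100 respondents and a mean of 2.5:

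- Protocol in 6 of the 10 and 6 of the 30: respondents (42 + 6)/100 = 48%; ICUs 12/40 = 30%; difference +18 points. Check: Cov = 48/40 − 2.5 × 0.30 = 0.45, and 0.45/2.5 = 0.18.
- Protocol in 3 of the 10 and 9 of the 30: respondents (21 + 9)/100 = 30%; ICUs 12/40 = 30%; difference 0.
- Protocol in 1 of the 10 and 9 of the 30: respondents (7 + 9)/100 = 16%; ICUs 10/40 = 25%; difference −9 points.

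With a milder imbalance (10 ICUs with 4 respondents and 30 with 2, protocol in 4 and 6 of them), respondents give (16 + 12)/100 = 28% against ICUs 10/40 = 25%, a difference of +3 points.

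The interval problem remains in the zero-difference case. With 10 ICUs of 7 and 30 of 1 and full agreement, deff = Σm²/Σm = (490 + 30)/100 = 5.2, the effective size is about 19, and coverage is about 61%.

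**The case against.** The strongest reply is that the SAP never says the denominator is respondents, and that the share of physicians reporting a protocol is a legitimate descriptive figure if labelled as such. Both points are fair. A respondent denominator is an inference, though a strong one: the sample is counted in respondents, no collapsing step exists, and the stated use of institution names leaves no room for one. The plan provides no such label either, and the aim points to ICUs.

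A reader might go further and infer that the reported implementation rate is certain to be biased, or that it will be too high because larger or more engaged units both reply more and have PBM. The documents do not support that. Nothing in them links respondent numbers to PBM or protocol status, and the examples run from +18 through 0 to −9 points on assumptions alone.

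Three further points stand. Using a PBM protocol may partly describe individual practice; the local protocol and the PBM clinic are the clearly institutional items. Grouping colleagues' answers goes beyond the purpose stated for institution names in an anonymous survey, so SAP wording alone is not enough. And one record per ICU cannot represent ICUs from which nobody replies.

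**Conclusion.** The point holds in this form: for the institutional items the plan leaves the unit of analysis undefined, and its natural reading gives respondent-weighted percentages with intervals computed as if colleagues' reports were independent.

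The interval is too narrow whenever several colleagues from one ICU tend to give the same answer. The loss is slight with 80 responding ICUs (about 92% coverage) and serious with 20 (about 62%), assuming an equal spread of 100 respondents and full agreement; unequal numbers make it worse and disagreement makes it milder. Bias in the percentage as an estimate of the ICU share is possible, not established, and its size and direction are unknown.

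The affected results are secondary endpoints of a descriptive survey. The primary endpoint, physicians' use of physiological parameters, can properly stay at physician level.

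**What to change.** In the SAP:

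- Analyse the local transfusion protocol and the existence of a PBM protocol with one record per ICU (institution plus department), and the PBM clinic with one record per institution.
- Report the number of responding ICUs and institutions, with exact or Wilson 95% intervals on those counts.
- Prespecify how discordant answers within a unit are resolved, including ties, and report within-unit agreement. A majority rule with ties shown as uncertain is one option, but it settles nothing when two colleagues from one unit disagree.
- Keep physician-level percentages for individual-practice items such as triggers, thresholds and one or two units, and label them as such.
- State how the ICU-level PBM value is attached to physician-level answers for the endpoint relating PBM to triggers.

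In Methods, amend the sentence on institution names so that they may also be used to group responses. Confirm that the single optional question is not the institution and department item; if it is, say how ungroupable responses are handled.

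No new data are needed, because the identifier is already on the questionnaire. The cost is a small protocol wording change, fewer units and wider intervals for these secondary endpoints, and results that still describe only the ICUs that responded.
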